5.3.2 Prohibited Concomitant Medications

The following treatments are prohibited during the treatment period of the study:

- Other investigational therapies (e.g., chemotherapy, radiation therapy, surgery, immunotherapy, biologic therapy, or hormonal therapy not required by this protocol) should not be given to patients. If such agents are required for a patient, then the patient must first be withdrawn from the study.
- Herbal preparations/medications are not allowed throughout the study unless approved by the Investigator. Herbal medications include, but are not limited to: St. John's wort, kava, ephedra (ma huang), ginkgo biloba, dehydroepiandrosterone (DHEA), yohimbe, saw palmetto, and ginseng. Patients should stop using herbal medications 7 days prior to first dose of study drug.
- While receiving quizartinib, concomitant medications that prolong the QT/QTc interval are prohibited except when regarded by the Investigator as essential for patient care (Appendix F and Appendix I).
- Strong CYP3A4 inhibitors are not prohibited, although quizartinib dose adjustments are required. Weak or moderate CYP3A4 inhibitors, such as fluconazole, may be used without dose reduction (Appendix H).
 - When treatment with a strong CYP3A4 inhibitor is initiated, reduce quizartinib one dose level (60 mg to 30 mg or 30 mg to 20 mg)
 - A patient taking a strong CYP3A4 inhibitor at enrollment will begin quizartinib treatment at 20 mg/day. The dose will be escalated to 30 mg/day at Day 15 of the maintenance phase if the QTcF interval is ≤ 450 msec prior to or at the Day 14 ECG evaluation.
- Concomitant strong or moderate CYP3A4 inducers are prohibited (Appendix H).
- Concomitant agents that prolong QTc are prohibited (Appendix I)

CONFIDENTIAL

If quizartinib is co-administered with drugs that inhibit P-glycoprotein (P-gp) or are substrates of P-gp, increased concentrations of quizartinib are possible and caution should be exercised. The co-administration of P-gp inhibitors and inducers with quizartinib should be avoided if possible.

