8.1 Criteria and Procedures for Dose Interruptions and Adjustments of Quizartinib

The following are reasons for quizartinib dose reduction or dosing interruption:

- Adverse event: QTcF prolongation, other non-hematologic toxicities, or myelosuppression
- Concomitant administration of a strong CYP3A4 inhibitor

Guidance on dose reductions and interruptions of quizartinib during the induction and consolidation phases as well as the maintenance phase are presented in Table 2 and Table 3, respectively.

The dose of quizartinib will not be reduced lower than 30 mg/day in any phase of the study (not lower than 20 mg/day for patients receiving strong CYP3A4 inhibitors. For AE toxicity management with concomitant strong CYP3A4 inhibitor, the dose of quizartinib will not be reduced lower than 20 mg/day refer to Table 2 for more information).

If quizartinib is interrupted, doses will not be made up.

Table 3 Dose Level Modifications – Induction and Consolidation Phases

Induction and Consolidation Phase				
Full Dose	AE, no concomitant strong CYP3A4 inhibitor	Concomitant strong CYP3A4 inhibitor	AE and concomitant strong CYP3A4 inhibitor	QTcF prolongation
30 mg/day	20 mg/day	20 mg/day	Interrupt ^a	See Section 8.2.1

^aRefer to Appendix F for duration of interruption. Missed doses will not be made up.

Table 4 Dose Level Modifications – Maintenance Phase

Maintenance Phase					
	Full Dose	AE, no concomitant strong CYP3A4 inhibitor	Concomitant strong CYP3A4 inhibitor	AE and concomitant strong CYP3A4 inhibitor	QTcF prolongation
Days 1-14	30 mg/day	20 mg/day	20 mg/day	Interrupt ^a	See Section 8.2.1
Days 15 onward	60 mg/day	40 mg/day ^b	30 mg/day ^c	30 mg/day ^d	See Section 8.2.1

CONFIDENTIAL

^aRefer to Appendix F for duration of interruption. Missed doses will not be made up.

^bCan be further reduced to 30 mg/day, if necessary

^cCan be further reduced to 20 mg/day, if necessary

^dCan be interrupted, if necessary

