Appendix F Management of Quizartinib-Associated Adverse Events

QTcF (QT interval corrected with Fridericia's formula) Prolongation

- Grade 1
 - Check magnesium and potassium levels and correct any abnormalities. If possible, stop any medications that may prolong the QTc interval. Continue quizartinib at the same dose.
- Grade 2 (QTcF average of triplicate readings >480 msec)
 - Check magnesium and potassium levels and correct any abnormalities. If possible, stop any medications that may prolong the QTc interval.
 - The dose will be reduced without interruption (See Table 2). Following dose reduction, the quizartinib/placebo dose may be resumed at the previous level in the next cycle if the QTcF has decreased to within 30 msec of baseline or <450 msec but subject must be monitored closely for QT prolongation for the first cycle at the increased dose.
 - If 20 mg/day is the current dose, dosing will be interrupted for up to 14 days. If QTcF returns to within 30 msec of baseline or ≤450 msec within 14 days, treatment may be resumed at 20 mg/day.
- Grade 3 (QTcF average of triplicate readings >500 msec)
 - Check magnesium and potassium levels and correct any abnormalities. If possible, stop any medications that may prolong the QTc interval.
 - Dosing will be interrupted for up to 14 days. If QTcF returns to within 30 msec of baseline or ≤450 msec within 14 days, treatment may be resumed at a reduced dose (See Table 2).
 - If 20 mg/day is the current dose, dosing will be interrupted for up to 14 days. If QTcF returns to within 30 msec of baseline or ≤450 msec within 14 days, treatment may be resumed at 20 mg/day. If Grade 3 event returns, treatment will be discontinued.
- Grade 4 (QTcF >500 msec or >60 msec change from baseline, and Torsade de pointes or polymorphic ventricular tachycardia or signs/symptoms of serious arrhythmia)
 - Treatment will be permanently discontinued.

Differentiation Syndrome

- Patients with suspected differentiation syndrome should promptly start treatment with systemic glucocorticoids and hemodynamic monitoring per local principal investigator or institutional preference until improvement. Treatment should be held until resolution to < Grade 3.

Non-Hematologic Toxicity

CONFIDENTIAL

STUDY DRUG: QUIZARTINIB
PROTOCOL DATE: 10 AUGUST 2020

DEVELOPMENT INNOVATIONS STUDY NUMBER: AML 48
VERSION 4.0

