Grade 3 or 4 non-hematologic toxicity that is at least possibly related to quizartinib and persisting >48 hours without improvement to \leq Grade 2 or without waiting 48 hours if in the Investigators judgment the AE poses a serious risk to the patient:

- Dosing will be interrupted for up to 28 days.
 - If toxicity improves to Grade ≤ 1 within 28 days, treatment may be resumed at the previous dose.
 - If toxicity improves to Grade ≤ 2 within 28 days, treatment may be resumed at a reduced dose (1 level) (See Table 2).
 - If toxicity does not improve/resolve within 28 days, then quizartinib will be discontinued.

Hepatic Events and Liver Enzyme Elevation

Elevation of liver enzymes that meet the criteria below should be investigated and the cause identified when possible:

- ALT $>8 \times$ ULN; or
- AST or ALT $>5 \times$ ULN for more than two weeks; or
- ALT or AST $>3 \times$ ULN, but not reaching the limits in the above criteria, in combination with clinical symptoms suggestive of hepatitis; or
- ALT or AST $>3 \times$ ULN with TBL $>2 \times$ ULN*
 - Combined elevations of ALT or AST with TBL as described above will be treated as Adverse Events of Special Interest and reported as per Section 11.2.*

Once the cause of liver enzyme elevation is identified, remove or treat the contributing cause. If the above criteria are met and the elevation is considered to be related or possibly related to quizartinib, then quizartinib dosing should be interrupted.

Liver enzyme level testing will be repeated at least weekly, or more frequently, based on degree of hepatic laboratory abnormality. If the liver enzyme levels return to baseline levels, quizartinib may be resumed at the full dose. If toxicity does not improve/resolve within 28 days, then quizartinib will be discontinued.

Upon resumption of quizartinib, if liver enzyme elevations recur, treatment may be resumed at a reduced dose following return to baseline levels.

Liver Safety Monitoring and Evaluations

Any patient who temporarily interrupts or permanently discontinues quizartinib due to confirmed liver enzyme abnormalities and/or jaundice in the absence of a known cause, must have an evaluation to determine the cause of the event.

Evaluation may include the following depending on the clinical situation:

- Medical history and physical exam, including focus on medications and substances used: alcohol, acetaminophen, azole antifungals, change in medication dosages, new

CONFIDENTIAL

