medications added, over the counter medication use and recreational drug use. Check for change in diet or use of dietary supplements

- Abdominal ultrasound
- Hepatitis B, and C screening (hepatitis B surface antigen, and anti-hepatitis C virus plus viral titer), antinuclear antibody and anti-Smith antibody, cytomegalovirus, Epstein Barr virus
- Additional evaluations as deemed appropriate by the Investigator to exclude other causes of liver enzyme and bilirubin elevations
- All laboratory results, including local laboratory reference ranges are to be recorded.

Myelosuppression (Maintenance Phase)

Quizartinib should be reduced or dosing interrupted (See Table 3) at the Investigator's discretion if:

- The patient has been treated for a minimum of 2 cycles;
- Platelet count is $<100,000/\text{mm}^3$ and $\text{ANC} \leq 1000/\text{mm}^3$; and
- There is no evidence of relapse.

The dose of quizartinib may be reduced stepwise from 60 mg/day to 30 mg/day to 20 mg/day. For patients experiencing myelosuppression requiring dose reduction while taking a dose of 30 mg/day (20 mg/day in patients receiving a strong CYP3A4inhibitor), dosing will be interrupted.

CONFIDENTIAL

STUDY DRUG: QUIZARTINIB
PROTOCOL DATE: 10 AUGUST 2020

DEVELOPMENT INNOVATIONS STUDY NUMBER: AML 48
VERSION 4.0

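### From maintenance Day 15, the dose-table cell for an adverse event with a strong CYP3A4 inhibitor repeats the 30 mg/day the patient already takes and omits the 20 mg/day step used in Appendix F

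*Combined protocol and SAP*

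**What the plan says.** **Dose on a strong inhibitor.** When a strong CYP3A4 inhibitor is started, Section 5.3.2 tells the site to "reduce quizartinib one dose level (60 mg to 30 mg or 30 mg to 20 mg"). For a patient already on one at enrollment, quizartinib starts at 20 mg/day and, if QTcF allows, "The dose will be escalated to 30 mg/day at Day 15 of the maintenance phase". By either route, the patient on an inhibitor is at 30 mg/day from Day 15 of maintenance.

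**Maintenance table in Section 8.1, Day 15 onward.** With a strong inhibitor and no AE, the entry is 30 mg/day, and footnote c allows a further reduction to 20 mg/day. With a strong inhibitor and an AE, the entry is again 30 mg/day, and footnote d allows interruption.

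**Floor in Section 8.1.** "For AE toxicity management with concomitant strong CYP3A4 inhibitor, the dose of quizartinib will not be reduced lower than 20 mg/day".

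**Appendix F, non-hematologic toxicity.** Grade 3/4 events that are at least possibly related and persist are first managed by interruption for up to 28 days. If the event improves to Grade 1 or better, the previous dose may be resumed. If it improves only to Grade 2, "treatment may be resumed at a reduced dose (1 level) (See Table 2").

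**Appendix F, myelosuppression in maintenance.** The dose may be stepped from 60 to 30 to 20 mg/day. The dose at which a further reduction becomes an interruption is 30 mg/day in general, but "20 mg/day in patients receiving a strong CYP3A4inhibitor), dosing will be interrupted".

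**The concern.** The patients in this cell have two reasons for caution at once: a co-medication that, according to Section 7.5.1, may raise quizartinib exposure, and an AE that calls for a dose change. For a patient already taking the inhibitor, the table returns the current dose as its answer to the AE. The lower step is printed beside the patient who has no AE.

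A site that works from the table would keep such a patient at 30 mg/day or interrupt. A site that works from Appendix F could reduce to 20 mg/day. The same toxicity could then be handled in different ways, each with support in the text. Safety and tolerability is a primary objective, and Section 1.5 describes QT prolongation with quizartinib as dose dependent, so the dosing instruction should be unambiguous.

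**Working it through.** The protocol gives no figure to reproduce here. The check compares the entries with one another and then with Appendix F.

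**Step 1. Effect of adding an AE for a patient on a strong inhibitor (both dose tables in Section 8.1).**

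| Row | Inhibitor alone | AE plus inhibitor | Effect of the AE |
|---|---|---|---|
| Induction and consolidation | 20 mg/day | Interrupt | Dosing stops |
| Maintenance, Days 1-14 | 20 mg/day | Interrupt | Dosing stops |
| Maintenance, Day 15 on | 30 mg/day (c: may go to 20) | 30 mg/day (d: may be interrupted) | 30 - 30 = 0 mg |

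The first two rows fit the floor. At 20 mg/day no lower dose is allowed, so interruption is the only step left. In the third row the patient is 30 - 20 = 10 mg above the floor. That is one dose level as Section 5.3.2 counts levels (30 to 20), and the AE cell does not offer it.

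**Step 2. The same patient under Appendix F, starting from 30 mg/day on a strong inhibitor.**

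| Event | Appendix F | Table cell | Agree? |
|---|---|---|---|
| Grade 3/4 non-hematologic, improves to Grade 1 or better within 28 days | Interrupt, then previous dose (30 mg/day) | 30 mg/day, may interrupt | Yes |
| Same, improves only to Grade 2 | Interrupt, then one level lower (20 mg/day) | 30 mg/day, may interrupt | No |
| Myelosuppression managed by reduction | 20 mg/day; interrupt if already at 20 | 30 mg/day, may interrupt | No |
| Myelosuppression managed by interruption | Allowed at the investigator's discretion | Allowed by footnote d | Yes |

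The disagreement in the second and third lines is 30 - 20 = 10 mg/day, one third of the dose being taken.

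**Step 3. Following the protocol's own steps.** From Day 15 the full dose is 60 mg/day. The inhibitor takes it to 30 (Section 5.3.2). A one-level AE reduction takes it to 20 (Appendix F), which is the floor in Section 8.1. After that only interruption remains. An entry of 20 mg/day with interruption if necessary would match this sequence.

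**QTcF prolongation is left out of the comparison.** Appendix F says for Grade 2 that "The dose will be reduced without interruption (See Table 2"), but the table gives QTcF its own column, which refers to Section 8.2.1. It is at most indirect support.

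**The case against.** **The floor is not breached.** A reader might infer that the cell contradicts the Section 8.1 sentence. It does not. That sentence sets a lower limit, and 30 mg/day lies above it. The cell only leaves out a step that the floor implies is available.

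**Something can still be done for the patient.** A reader might infer that a patient with an AE is left without any action. Footnote d allows interruption. Section 8.2 sends AE management to Appendix F, where interruption is the first response to Grade 3/4 non-hematologic toxicity and is also open to the investigator for myelosuppression. This stands. What the cell lacks is a reduction, not every response.

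**The cell is a real reduction for some patients.** A patient already cut to 40 mg/day for an AE who then starts a strong inhibitor would go to 30 mg/day. A patient at 60 mg/day who meets both conditions together would also go to 30, although that equals the cut for the inhibitor alone. The fault therefore concerns the patient who is already on the inhibitor when the AE occurs.

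**The scope is narrow.** Induction, consolidation and maintenance Days 1-14 are consistent, so the point does not extend to maintenance as a whole.

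**Size.** Because the row runs from Day 15 of Cycle 1 to the end of Cycle 24, and Section 5.3.1 names voriconazole as an example of routine antifungal prophylaxis, a reader might infer that most patients are affected. The documents do not support that. The cell applies only when a strong inhibitor and an AE needing a dose change coincide. Section 5.3.1 also allows other antifungals, and Section 5.3.2 requires no reduction with fluconazole. No usage rate is given.

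**Table numbers.** The captions read 3 and 4 while the text cites Tables 2 and 3. The List of Tables agrees with the citations, and the captions name the phase, so this is clerical.

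**Conclusion.** The point holds for one cell: maintenance, Day 15 onward, AE together with a strong CYP3A4 inhibitor. For a patient already on the inhibitor, the entry gives a 0 mg reduction where Appendix F gives 10 mg (30 to 20 mg/day) in two situations: non-hematologic toxicity that improves only to Grade 2, and myelosuppression managed by reduction. The footnote that permits 20 mg/day sits on the column where it is less needed. This is an internal inconsistency in a dosing instruction, with some bearing on patient safety.

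The conclusion assumes that one level below 30 mg/day is 20 mg/day, as Section 5.3.2 counts it, and that the patient was on the inhibitor before the AE. The number of patients affected cannot be derived from the protocol.

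A reader might also infer harm to the efficacy result or the stopping rules, but neither is shown. Section 10.4.2 counts response at the recovery assessment, and the lead-in rules rest on delayed count recovery and Grade 4 events. Section 10.4.3 lists no dose-intensity analysis, and differences between sites are a possibility, not a finding.

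**What to change.** In the Day 15 onward row of the maintenance table, do one of the following, subject to confirmation by the sponsor's clinical team:

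- change the cell to 20 mg/day and keep footnote d; or
- keep 30 mg/day and attach footnote c alongside footnote d.

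The first makes 20 mg/day the stated AE dose for a patient already at 30. It would also send a patient at 40 mg/day for an AE straight to 20 on starting a strong inhibitor, so the sponsor should check that this is intended. The second keeps 30 mg/day for that patient and makes the 20 mg/day step available to both.

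As housekeeping, renumber the two captions to Tables 2 and 3, to match the List of Tables and the citations.

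The cost is one cell or footnote mark and two caption numbers in the next amendment. No patients, procedures or analyses change.

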8.2 Management of Quizartinib-Associated Adverse Events

Management for quizartinib-associated AEs is located in Appendix F.

8.2.1 Criteria and Procedures for Dose Modification due to QTcF Prolongation

Electrolytes (potassium and magnesium) should be checked and supplementation given to correct any values outside the normal range. Concomitant medications should be reviewed to identify and, if appropriate, discontinue any medication with known QT prolonging effects (see Appendix F). In addition hypomagnesemia, hypokalemia, and hypomagnesemia abnormalities can affect the QT interval. Upon identification of QTcF prolongation, it is advised to assess the subject's electrolytes (including potassium and magnesium) and manage per local institutional standards.

Patients who experience >480 msec QTcF prolongation and undergo dose interruption and/or reduction must be monitored closely with ECGs, performed twice weekly for the first week of the QTcF prolongation and then weekly thereafter until the QTcF prolongation is resolved. If QTcF is > 450, evaluation of concomitant medications and electrolyte levels (including potassium and magnesium) are advised to assess for potential etiologies. Repeating ECGs daily for up to 3 days can occur to determine if the QTcF improves to allow administration of quizartinib.

8.3 Management of CPX-351-Related Adverse Events

Management for CPX-351-related AEs is located in Appendix G.

8.3.1 Criteria and Procedures for Dose Interruptions and Adjustments of CPX-351

If a patient develops non-hematologic Grade ≥ 3 AE(s) without resolution by 28 days from the first administration, or develop prolonged hematologic toxicities Grade ≥ 3 without count recovery 56 days or longer from first administration, the AEs will be considered severe AEs. However, this will not remove the patient from staying on study to receive quizartinib unless the PI believes quizartinib will exacerbate or prolong the toxicity.

9. RESPONSE EVALUATIONS AND MEASUREMENTS

9.1 Complete Response (CR)

A CR will be defined as no morphologic, immunohistochemical, or flow cytometric evidence of disease by BM biopsy/aspirate and a peripheral CBC with platelet count $\geq 100,000/\mu\text{L}$ and ANC $\geq 1000/\mu\text{L}$ at the time of the bone marrow biopsy/aspirate. A molecular CR (CR_m) is defined as having no evidence of disease by BM biopsy/aspirate by morphology, immunohistochemistry, flow cytometry, and FLT3 mutation by MRD analysis. Patients with a CR but with residual MRD positivity (CR MRD⁺) are classified as indicated.

CONFIDENTIAL

STUDY DRUG: QUIZARTINIB
PROTOCOL DATE: 10 AUGUST 2020

DEVELOPMENT INNOVATIONS STUDY NUMBER: AML 48
VERSION 4.0

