6.3 Central Nervous System (CNS) Prophylaxis

Patients with a history of CNS involvement of leukemia, with monocytic differentiation, or with a WBC >40,000 cells/ μ L should receive a lumbar puncture using either intrathecal (IT) methotrexate or cytarabine, following site-specific standard operating procedures during the first induction cycle of CPX-351 with quizartinib.

The CNS prophylaxis regimen may be modified by the attending physician in consultation with the PI as clinically indicated. No further IT chemotherapy is required in this study if there is no evidence of disease. However, additional administrations, per the treating physician or per institutional standard operating procedures, are permitted.

In patients who have CNS disease involvement, IT chemotherapy should continue every 4 days (\pm 1 day) until disease clearance, followed by every 7 days (\pm 2 days) for 2 additional administrations. Thereafter, administer IT chemotherapy every 28 days (\pm 7 days) for at least 12 cycles.

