9.2 Complete Response with Incomplete Hematologic Recovery (CRi)

A CR with incomplete hematologic recovery (CRi) is defined as no morphologic, immunohistochemical, or flow cytometric evidence of disease by BM biopsy/aspirate, but with a persistent platelet count $<100,000/\mu\text{L}$ and/or ANC $<1000/\mu\text{L}$ at the time of BM biopsy/aspirate.

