9.6 Time-to-Progression (TTP)

Time-to-progression is defined as the number of days between diagnosis of relapse or refractory AML to disease progression, confirmed by bone marrow biopsy.

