9.7 Event-free Survival (EFS)

Event-free survival is calculated as the number of days from the first date of treatment to the first date of evidence of PD by BM biopsy/aspirate, or death, regardless of cause. Patients who are alive without a disease response assessment of relapsed disease will be censored at the last adequate disease assessment date. Patients without a disease response assessment will be censored at the first date of treatment. This calculation does not pertain to Long Term Follow-up data.

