9.8 Recurrence of Disease

Recurrent malignancy will be defined by hematologic criteria. Recurrent malignancy will also be defined as any unplanned medical intervention designed to prevent progression of malignant disease in patients who have molecular, cytogenetic, or flow cytometric evidence of malignant cells after transplantation.

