Appendix E ASBMT RFI 2017 – Disease Classifications Corresponding to CIBMTR Classifications

ASBMT Diagnosis Category	ASBMT RFI Classification	CIBMTR Classification [^]
AML and ALL precursor B-lymphoblastic lymphoma/leukemia {per W.H.O. reclassified from lymphoma} precursor T-lymphoblastic lymphoma/leukemia	Low risk: CR 1	First complete remission (CR1): A treatment response where all of the following criteria are met for at least four weeks* [†] : 
 • Hematological: no blast cells in the peripheral blood, < 5% blasts in the bone marrow, no blasts with Auer rods (AML only), normal maturation of all cellular components in the marrow, normal CBC and ANC of > 1,000/μL • Platelets \geq 100,000/μL*[†] • Transfusion independent • No other signs or symptoms of disease, including extramedullary disease(e.g., central nervous system or soft tissue involvement) 
 • Include recipients with persistent cytogenetic abnormality who otherwise meet all the criteria of CR. CIBMTR collects information about cytogenetic and molecular testing for those in CR (hematologic CR), however these are only relevant for RFI reporting in as much as the centers judge importance of residual cytogenetic abnormalities in determining current status beyond the hematic criteria. • *In some cases, there may not be a four-week interval between the completion of treatment for disease and the disease assessment immediately prior to the HSCT. If this is the case, CR should still be reported as the status at transplantation. Although this is an exception to the general condition that CR is “durable” beyond four weeks, the status of CR represents the “best assessment” prior to HSCT. Similarly, sufficient time may not have elapsed to allow for platelet recovery to normal levels and physician judgment is required to interpret whether residual low platelet counts may reflect residual disease. 
 
NOTE: Recipients with MDS that transformed to AML If the recipient has residual MDS following treatment for AML, report the AML disease status as either PIF or relapse (i.e., the recipient cannot be in an AML CR if there is evidence of MDS at the time of assessment).
 

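### CR, CRi and progression are scored from marrow and counts alone, although CNS leukemia is foreseen on study and Appendix E treats extramedullary disease as incompatible with CR

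*Combined protocol and SAP*

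**What the plan says.** **Response.** Section 9.1 reads "A CR will be defined as no morphologic, immunohistochemical, or flow cytometric evidence of disease by BM biopsy/aspirate and a peripheral CBC with" adequate platelets and ANC. Section 9.2 defines CRi as "no morphologic, immunohistochemical, or flow cytometric evidence of disease by BM biopsy/aspirate, but with a persistent platelet count" or ANC below the CR threshold. Neither section mentions CNS or other extramedullary disease. Section 2.3.1 cites the revised International Working Group criteria for CR and CRi, but spells out only morphology and counts. Under Section 10.4.2 the primary ORR is the proportion in CR or CRi at the recovery assessment.

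**Progression and relapse.** TTP (9.6) ends at "disease progression, confirmed by bone marrow biopsy". EFS (9.7) runs "to the first date of evidence of PD by BM biopsy/aspirate" or death from any cause. Patients alive without an assessment showing relapse are censored at the last adequate disease assessment, and long-term follow-up data are not used. DOR (9.5) ends at relapse, with no stated limit to marrow. Section 9.8 begins "Recurrent malignancy will be defined by hematologic criteria" and then adds a second route, for certain unplanned interventions after transplantation.

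**Population.** The exclusions in Section 3.2 do not list CNS or extramedullary leukemia. Section 6.3 foresees it: "In patients who have CNS disease involvement, IT chemotherapy should continue every 4 days".

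**Appendix E.** The CR definition there requires "No other signs or symptoms of disease, including extramedullary disease(e.g., central nervous system or soft tissue involvement"), and extramedullary disease appears in its list of what constitutes relapse. The protocol applies Appendix E at baseline (6.2) and in long-term follow-up (6.4.6). It is not linked to Sections 9.1 to 9.8.

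**The concern.** The protocol admits patients who may have leukemia outside the marrow, yet its endpoint definitions look only at marrow and blood counts. Two errors can follow, both in the favourable direction.

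- A patient whose marrow has cleared while documented CNS or soft-tissue disease remains active meets 9.1 or 9.2 and adds one to the primary response count.
- A patient who relapses only outside the marrow has no TTP event and no EFS event at that time. If alive, the patient is censored for EFS at the last adequate assessment. That censoring is informative, because it is prompted by the kind of failure the endpoint should record.

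The protocol also holds two incompatible standards. Appendix E would not call the first patient a CR and would call the second a relapse. Because 9.7 bars long-term follow-up data, the stricter standard cannot correct EFS later. In an open-label, single-arm trial at about five sites, whose primary test is a count of responders, scoring should not depend on how each site fills this gap.

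**Working it through.** **1. Definitions side by side**

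| Item | Stated basis | Extramedullary disease addressed? |
|---|---|---|
| CR (9.1), CRi (9.2) | Marrow, ANC, platelets | No |
| TTP (9.6) | Progression confirmed in marrow | No |
| EFS (9.7) | Progression in marrow, or death | No, except through later death |
| DOR (9.5) | Relapse, site not stated | Open |
| Recurrence (9.8) | Hematologic criteria, or certain unplanned post-transplant interventions | In part, after transplant |
| Appendix E | Marrow, counts and no extramedullary disease; extramedullary disease is relapse | Yes |

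DOR may therefore end at an event that TTP and EFS do not record.

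**2. What is already collected.** The recovery visits (6.4.1.5 and 6.4.1.10) schedule physical examination, counts and marrow, but no CSF sample. Section 6.3 calls for lumbar puncture in selected patients during the first induction cycle. Some extramedullary disease will therefore be documented from existing procedures, but it will not be sought systematically at response.

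**3. The plan's own figures.** Inputs from Section 10.2: n = 30 evaluable, reject at 13 or more responses, null rate 0.27, alternative 0.50, one-sided target 0.05, 10% non-evaluable.

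P(X ≥ 13) = Σ, k = 13 to 30, of C(30,k) p^k (1−p)^(30−k)

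- p = 0.27: 0.0395, within the 0.05 target. With a boundary of 12 it would be 0.0845, so 13 is the right boundary.
- p = 0.50: 0.8192, consistent with the stated 80% power.
- Enrolment: 30/0.9 = 33.3, rounded up to 34.

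All stated figures reproduce, and this point does not challenge them.

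**4. Sensitivity to misclassification.** One patient is 1/30 = 3.3 points. Let m be the share of patients scored CR or CRi with a clear marrow but active extramedullary disease. The documents give no value for m, so every row except m = 0 is an assumption. With a true rate of 0.27, the chance of rejecting is P(X ≥ 13) at p = 0.27 + m:

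| m | p | P(13 or more of 30) |
|---|---|---|
| 0 | 0.27 | 0.0395 |
| 1 point | 0.28 | 0.0518 |
| 2 points | 0.29 | 0.0667 |
| 3 points | 0.30 | 0.0845 |

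This treats the 27% benchmark as a rate that excludes such patients. The documents do not give the benchmark study's response definition, so that too is an assumption.

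**The case against.** The strongest objection is that Section 2.3.1 defines CR and CRi by reference to published criteria that might themselves deal with extramedullary disease. Those criteria are not reproduced, so this cannot be settled from the documents. It does not close the gap, because Section 9 does not invoke them. Sections 2.3.1 and 9.1 also already differ: 2.3.1 has a CR category with residual disease detected by flow, whereas 9.1 requires no flow evidence of disease. The protocol has to say which text governs.

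Several stronger readings are tempting, and the documents do not support them:

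- *An extramedullary relapse can never lead to an EFS event.* Later death counts as an event, and a living patient is censored rather than carried forward as event-free. Section 6.4.5 also has patients complete the study at PD without limiting PD to marrow.
- *DOR is marrow-only.* Its start is a marrow finding, but its end is relapse with no site specified. The fault is inconsistency with TTP and EFS.
- *Section 9.8 excludes all such relapses.* Its second sentence names no site and could capture some post-transplant cases, provided an unplanned intervention took place.
- *Up to 10 points of ORR are at stake.* If 3 to 10% of 30 patients had extramedullary disease (assumption), that is 0.9 to 3 patients. Reaching 10 points needs all of them to be marrow responders with disease still active elsewhere at recovery. At the 50% target response rate the range is 0.45 to 1.5 patients. If half of those remained positive (assumption), it is about 0.2 to 0.75.
- *Appendix E directly contradicts an on-treatment CR.* It is a registry classification used at baseline and follow-up, and a CR on treatment followed by a later relapse can both be true. The conflict is that the two standards would classify the same findings differently.

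It is also fair to say that entry requires more than 5% blasts and a marrow diagnosis. Isolated extramedullary disease does not enter, and the response question concerns disease that accompanies marrow involvement.

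**Conclusion.** The point holds on the operative text. As written, a patient with documented active extramedullary leukemia and a clear marrow counts toward the primary ORR, and an extramedullary-only relapse is not itself a TTP or EFS event. Appendix E shows that the protocol elsewhere adopts the opposite standard.

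The direction of any bias is favourable, but its size is unknown, because the documents give neither a rate of extramedullary disease nor a clearance rate. A reader might infer that ORR is shown to be overstated; the documents show only that the stated rules permit it. What can be said is that each misclassified patient is 3.3 points, and that one added point on a true 27% would take the type I error just past its 0.05 target (0.0518), if the benchmark excludes such patients. The change should be made: the definitions carry the primary test, and the repair is cheap.

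**What to change.** - State in Section 9 whether the response criteria cited in 2.3.1 govern, and reconcile 2.3.1 with 9.1 and 9.2.
- Add to 9.1 and 9.2: *and no documented extramedullary disease, including CNS*, judged from physical examinations and any lumbar punctures already done under the protocol.
- In 9.6 and 9.7, count documented extramedullary relapse or progression as an event on the date it is found.
- Make 9.5 and 9.8 use the same relapse definition as Appendix E, so that DOR, TTP and EFS treat the same relapse alike.

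The cost is definition wording and one eCRF item. There is no new procedure, no change to the 13-of-30 rule or to enrolment, and no change to treatment. Limiting the condition to documented disease is what avoids new procedures, at the price of missing disease that nobody looked for.

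The downside is that ORR and EFS may be slightly less favourable. If the true marrow-based rate were 50% and the added condition removed 1, 2 or 3 points (assumption), power would fall from 0.8192 to 0.7888, 0.7555 or 0.7196.
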